#### **5.2.4. Treatments in the Open-Label Phase**

Though tofacitinib 10 mg BID dose is no longer evaluated in this study, a dose increase from 5 mg BID to 10 mg BID was allowed based on previous protocol for individuals who are unable to control fever within the first 2 weeks of treatment with tofacitinib 5 mg BID in Part 1, at the investigator's discretion. These dose switchers will be grouped together with the other pure 5 mg BID treated subjects for the OL phase analyses, with the number of dose switchers footnoted in related TFLs.

#### **5.2.5. Treatments in Double-Blind Withdrawal Phase**

At the beginning of the double-blind randomized withdrawal phase, subjects from the open-label run-in phase will be randomized into 2 sequences: tofacitinib 5 mg BID (continuation of tofacitinib treatment), or placebo (withdrawal of tofacitinib). In the primary and secondary double-blind analyses, the two treatment groups (tfacitinib or placebo) will be compared to assess the treatment effect. Some descriptive analyses will be performed.

### **5.3. Methods to Manage Missing Data**

In general, missing values will not be imputed for descriptive statistics. In addition, missing values for safety endpoints will not be imputed and no data in the open-label phase analyses will be imputed, except for derivations of specific variables outlined below. For the endpoints not mentioned in the following sections, missing data will not be imputed. As limited number of subjects were enrolled with short follow up time in the double-blind phase before the COVID-19 pandemic anchor date, the impact of COVID-19 pandemic is limited. Missing due to COVID-19 pandemic will be treated the same way as the other missing data.

#### **5.3.1. Disease Flare**

Disease flare in the double-blind phase will be assessed in real-time by the Centralized Coordinating Center (CCC) according to the CCC's SOP and used in the analyses.

Every effort will be made to collect the components required for the real-time flare calculation. Per CCC's SOP, in the event that individual JIA core set components are missing at a given double-blind visit (while the subject is still ongoing in the DB) and that the available data are inconclusive for the determination of flare, the CCC will utilize the missing component(s) value from the previous visit. This type of mixed components LOCF method is based on calculating the composite value using a mixture of values at a visit and values carried forward from previous visits, which may include the double-blind baseline if no post-baseline values are available.

Different imputation methods of disease flare dates for the censored data are described separately in [Sections 6.1.1, 6.1.2.1](#) and [6.1.2.2](#).

### **5.3.1.1. Censoring Times and Risk Periods for Disease Flare**

The first event will be counted within the defined risk periods below. If a subject does not have an event or has an event but outside the risk period, the subject will be censored at the last available flare assessment within the risk period. Subjects with no post-randomization flare assessments will be censored at randomization date.

Define last contact date as the maximum of (last study visit date, subject withdrawal from study date, telephone contact date). If a subject dies, last contact date is the death date.

#### On-Treatment Censoring Time and Risk Period

The risk period corresponding to the on-treatment censoring time is defined from the date of the randomization to the minimum of (last contact date, last investigational product dose date + 2 days). The addition of 2 days to the last investigational product dose date permits the data collected 2 days after the last investigational product dose be considered as on-treatment. Explicitly, the risk period is calculated as the minimum of (last contact date, last investigational product dose date + 2 days) – date of randomization + 1.

This risk period will be used in the primary analysis (Estimand 1) and a supplementary analysis (Estimand 4) for time to disease flare.

#### On-Study Censoring Time and Risk Period

The risk period corresponding to the on-study censoring time is defined from the date of the randomization to the last contact date. Explicitly, the risk period is calculated as the last contact date – date of randomization + 1. For subjects who withdraw from study early, before reaching 52 weeks of double-blind treatment from Study A3921165 and enrolled in the LTE study (Study A3921145), the last contact date will be extended to the upper limit of the DB Week 52 visit window post randomization through both studies A3921165 and A3921145 (ie, Randomization Day + 378) (See [Appendix 3.13](#)).

This risk period will be used in a supplementary analysis (Estimand 5) for time to disease flare.

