Subjects will be enrolled into an open-label phase during which they will receive tofacitinib 5 mg twice daily (BID) oral tablets, or an equivalent weight-based lower dose of tofacitinib oral solution (1 mg/mL) BID for subjects <40 kg. The 5 mg BID dose level of tofacitinib will be evaluated in a staggered fashion (cohorts of 7 subjects followed by safety review), as described under “Dose Selection” in [Section 3.4](#).

The open-label phase will be divided into two parts. In Part 1, all subjects must achieve and maintain a minimum level of clinical response for at least 4 weeks. In Part 2 of the open-label phase, subjects treated with background CSs >0.2 mg/kg/day oral prednisone (or equivalent) must taper their CS dose to a target range. Subjects who successfully taper their CS dose while maintaining the defined clinical response, will be eligible for the double-blind withdrawal phase of the study. The minimum total duration of treatment with a stable dose of tofacitinib for subjects completing Parts 1 and 2 must be 12 weeks to qualify to enter the randomized withdrawal phase of the study.

In the double-blind withdrawal phase, “responders” from the open-label phase will be randomized in a 1:1 ratio to either continue tofacitinib or start placebo. The primary endpoint of the study is time to sJIA flare in the double-blind phase.

Subjects who flare or achieve ACR clinical remission (ie, maintain JIA ACR inactive disease during 24 consecutive weeks) will be given the opportunity to participate in A3921145 and be treated with open-label tofacitinib.

[figure not shown]
Subjects who discontinue Investigational Product in the double-blind phase and who do not enter A3921145 will continue in A3921165 for follow up of efficacy and safety endpoints. Subjects will be required to perform all scheduled visits until Week 52 after randomization or until the study concludes, whichever comes first. Subjects should receive standard-of-care treatment in accordance with local treatment guidelines.

All subjects participating in this study, including those discontinued, will have the option, if eligible, of enrolling in the tofacitinib long-term extension study (A3921145). The Sponsor's intent is to make tofacitinib available to pediatric subjects through Study A3921145.

Subjects who discontinue the study in the Open-Label Phase and do not enter A3921145, will be required to perform a follow-up visit 28 days after the last dose of study treatment.

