After randomization, subjects will be required to maintain a stable dose of CSs during the withdrawal phase. Subjects who flare at any time during the randomized withdrawal phase, or who experience 24 consecutive weeks of inactive disease as assessed using JIA ACR (clinical remission) (Wallace 2011)¹⁶, will complete their participation in the study. An end-of-study visit should be performed. Subjects who discontinue Investigational Product in the double-blind phase of the study due to any reason will be counted as having an sJIA flare in the primary analysis for the primary endpoint of the study and will contribute to the requisite number of subjects with flare for the study to be considered complete. Subjects who achieve clinical remission are completers of the study and will not be counted as having an sJIA flare in the primary analysis. Upon notification by the Sponsor, an end-of-study visit should be scheduled for all remaining subjects in the study in accordance with [Section 6.8](#).

All subjects participating in this study, including those discontinued from the study, will have the option, if eligible, of enrolling in the tofacitinib long-term extension study (A3921145). The Sponsor’s intent is to make tofacitinib available to pediatric subjects through Study A3921145.

Subjects who discontinue Investigational Product in the double-blind phase for reasons other than sJIA flare, and who do not enter A3921145 are required to continue in the study and perform all scheduled visits until Week 52 after randomization or until the study concludes, whichever comes first. Such subjects should transition to standard-of-care treatment in accordance with local treatment guidelines.

[figure not shown]
3.4. Sequential Evaluation of Tofacitinib 5 mg BID Dose in Cohorts in Part 1

Dosing will not exceed 5 mg BID, which is the approved dose for adult RA patients.

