6.7. Double-blind Withdrawal Phase: Visits Every 4 Weeks after Randomization Visit

After randomization in the double-blind withdrawal phase, each subject will have visits on a monthly basis until they experience a sJIA flare, or experience 24 consecutive weeks of inactive disease as assessed using JIA ACR (clinical remission), or until the requisite number of flares have been reported (refer to [Section 11](#)) and the study is considered completed.

The procedures and assessments listed below will be performed at every visit of the double-blind withdrawal phase. The window for these visits is ± 5 days.

- Evaluate concomitant medications. Refer to [Section 5.8](#).
- Targeted physical exam, including skin examination for chickenpox or shingles.
- Perform a risk factor check for venous thromboembolism. Refer to [Section 8.2.13](#) for details.
- Vital signs, height and weight.
- Review temperature diary and assess “Fever” and “Absence of fever”:
 - Obtain subject’s oral temperature and assess “Fever”, defined as temperature $>38^{\circ}$ C/100.4° F;
 - **MAS diagnosis: Only if subject has fever and MAS is suspected:** obtain blood samples to evaluate Ferritin, Platelets, Triglycerides and Fibrinogen levels. Refer to [Section 8.2.11](#) for details regarding these blood sample collections;
 - Evaluate “Absence of fever”, defined as documented absence of fever due to systemic JIA in the week preceding this visit. Record the outcome in the eCRF for calculation of the Adapted JIA ACR response.
- Assess the sJIA Disease Activity status:
 - Fever (see above);
 - Number of joints with limitation in range of motion;
 - Number of joints with active arthritis (swelling and/or pain/tenderness);
 - Assess duration of morning stiffness;
 - Assess extra-articular sJIA manifestations: rash, serositis, splenomegaly, hepatomegaly, or generalized lymphadenopathy attributable to sJIA;
 - Uveitis status: document presence/absence of active uveitis;
 - Physician’s Global Assessment of Overall Disease Activity;
 - Administer the Childhood Health Assessment Questionnaire (CHAQ); evaluate Patient wellbeing as part of the CHAQ on a 21 circle VAS;
 - Only every 6 months after the randomization visit: Administer Child Health Questionnaire;
 - ESR determination (utilizing ESR test kit provided by Sponsor); record result on appropriate CRF.

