### 2.3.3. Additional Estimands for Primary Endpoint

A supplementary (Estimand 4) estimand for the primary endpoint will use the hypothetical strategy, which estimates the treatment effect if all patients adhere to the protocol and the intercurrent event of investigational product discontinuation has not occurred. It differs from the primary estimand in the following 2 attributes:

- Variable: time to sJIA disease flare in the double-blind phase.

Patients who discontinue from investigational product for reasons other than flare in the double-blind phase and who complete study participation after achieving clinical remission, will be considered as non-flare and censored at the last available flare assessment while on investigational product. (More details of on-treatment censoring time and risk period are provided in [Section 5.3.1.1](#).)
- Intercurrent event: all data after an intercurrent event (investigational product discontinuation), if collected, will be excluded.

A second supplementary estimand (Estimand 5) for the primary endpoint will use the treatment policy strategy and estimate the treatment difference regardless of whether an intercurrent event occurs. It differs from the primary estimand in the following 2 attributes:

- Variable: time to sJIA disease flare in the double-blind phase.

- Intercurrent event: investigational product discontinuation is not considered for analysis. All the flare data collected both on-treatment and off-treatment in the double-blind phase of Study A3921165 will be used. For subjects who withdraw from study early, before reaching 52 weeks of double-blind treatment from Study A3921165 and enrolled in the LTE (Study A3921145), the flare data collected through Week 52 post randomization from both studies A3921165 and A3921145 will be included (see [Section 6.1.2.1](#)). (More details of on-study censoring time and risk period are provided in [Section 5.3.1.1](#).)

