#### **6.1.2. Supplementary/Sensitivity Analyses**

##### **6.1.2.1. Supplementary Analyses**

###### Supplementary Analysis 1

- Estimand strategy: hypothetical ([Section 2.3.3](#)).
- Analysis set: DBFAS ([Section 4.1.1](#))
- Analysis methodology: methods described in Section 5.2.1.
- Censoring time and risk period: On-Treatment Censoring Time and Risk Period ([Section 5.3.1.1](#)).
- Intercurrent events and missing data: See definitions described in Section 2.3.3 for intercurrent events; and Section 5.3.1 for missing values.

###### Supplementary Analysis 2

- Estimand strategy: treatment policy ([Section 2.3.3](#)).
- Analysis set: DBFAS ([Section 4.1.1](#))

- Analysis methodology: methods described in [Section 5.2.1](#).
- Censoring time and risk period: On-Study Censoring Time and Risk Period ([Section 5.3.1.1](#)).
- Intercurrent events and missing data: See definitions described in [Section 2.3.3](#) for intercurrent events; and [Section 5.3.1](#) for missing values.

Supplementary Analysis 2 will include observations that occur after the intercurrent event of investigational product discontinuation. Subjects discontinuing investigational product in the double-blind phase, for reasons other than flare, before reaching 52 weeks of double-blind treatment will continue to be followed up for flares either via scheduled study visits in this study or in the LTE study A3921145 (for subjects who withdraw from this study and roll over) for up to 52 weeks post randomization. For data coming from A3921145 study, disease flare will be programmatically evaluated using the same approach by CCC as in this study. Flares occurring after investigational product discontinuation in A3921165 study come from either the CCC flare assessment at regularly scheduled study visits or the follow-up visit post investigational product discontinuation.

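### Supplementary Estimand 5 is labelled treatment policy, but its follow-up horizon depends on product status, so after about Day 378 it is essentially an on-product comparison

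*SAP*

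**What the plan says.** SAP 2.3.3 defines Estimand 5, the second supplementary estimand for time to flare, under a treatment-policy strategy: "investigational product discontinuation is not considered for analysis". It adds: "All the flare data collected both on-treatment and off-treatment in the double-blind phase of Study A3921165 will be used".

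SAP 5.3.1.1 gives the risk period: "The risk period corresponding to the on-study censoring time is defined from the date of the randomization to the last contact date". For a child who leaves early and enters A3921145, "the last contact date will be extended to the upper limit of the DB Week 52 visit window post randomization", written as Randomization Day + 378.

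How long a child is actually observed is set elsewhere:

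- **Off product, remaining in this study** (Protocol Summary and 3.1): "Subjects will be required to perform all scheduled visits until Week 52 after randomization or until the study concludes, whichever comes first".
- **Off product, either study** (SAP 6.1.2.1): follow-up for flare lasts "for up to 52 weeks post randomization".
- **On product** (Protocol 6.7): "each subject will have visits on a monthly basis until they experience a sJIA flare, or experience 24 consecutive weeks of inactive disease", or until the required number of flares is reached.

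The SAP's other treatment-policy estimands, Estimand 3 (2.3.2.2) and Estimand 6 (2.3.4), use on- and off-product data to Week 52 for every child.

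**The concern.** A treatment-policy analysis should keep a child in the risk set after product is stopped, for as long as comparable children are kept. Here stopping product shortens the time a child can contribute. Up to Week 52 the rule works. After that, off-product children drop out of the risk set and on-product children remain, so the log-rank test and the Cox model combine a treatment-policy comparison with a later on-product one.

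This matters because the primary analysis counts almost every discontinuation as a flare. Estimand 5 is the analysis a reader will use to see what happens when that rule is lifted. As specified, it is neither a 52-week treatment-policy effect nor one over the whole study.

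**Working it through.** **1. Last flare data usable under Estimand 5, by product status**

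| Child | Data end at |
|---|---|
| Stops before Week 52, stays in A3921165 | Week 52, or study end if earlier |
| Stops before Week 52, enters A3921145 | Randomization Day + 378 |
| Stops after Week 52 | No further scheduled visits required; at most a follow-up visit about four weeks after the last dose (Protocol 6.9) |
| Still on product | Flare, clinical remission or study end |

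So person-time beyond about Day 378 is essentially on-product in both arms.

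**2. The plan's own figures reproduce.** Inputs: HR 0.36, placebo median 236 days, one-sided alpha 0.025, looks at 28 and 37 flares, gamma spending 4 (efficacy) and -4 (non-binding futility) (SAP 5.1, Table 2). A two-look log-rank calculation with information d/4 gives boundaries 1.973 and 1.240, a final boundary of 2.586 (absolute values) and power 80.4%, all as stated. Exponential flare times with Protocol 10.1.1 accrual (23 randomized over 225 weeks, then 0.315 per week to 54) give 19.9 flares at Week 262 and 39.8 at Week 358. The protocol plans for 20 and 40.

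**3. Share of flares after Day 378.** Placebo hazard = ln 2/236 = 0.002937 per day.

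- Placebo flare-free at Day 378: exp(-0.002937 × 378) = 0.33.
- Tofacitinib: exp(-0.36 × 0.002937 × 378) = 0.67.
- At Week 358 with no discontinuation: 39.75 flares expected, 26.55 of them by Day 378. The rest is 13.2, or 33%. Cutting at the 37th flare instead gives 32%.

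These are upper figures. Discontinuations count towards the required flares, so the trial ends sooner. With that included, about 25% of flares fall after Day 378 at an assumed 20% per year stopping product, and 22% at 30%. With assumed remission exits of 0.3 (placebo) and 0.5 (tofacitinib) per year and a Week 358 cut, the share is 18%.

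**4. Effect on the hazard ratio.** Large-sample Cox fits; on-product HR 0.36. Off-product hazards are multiples of the placebo hazard. Stopping rates, off-product hazards and frailty are assumptions, because the documents give none.

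| Stop rate per year (placebo/tofacitinib) | Off-product hazard (placebo/tofacitinib) | As planned | Cap at Day 378 | Everyone to study end |
|---|---|---|---|---|
| 0 | n/a | 0.362 | 0.360 | 0.362 |
| 15%/15% | 0.36/0.36 | 0.374 | 0.378 | 0.416 |
| 15%/15% | 1.0/1.0 | 0.384 | 0.395 | 0.412 |
| 15%/15% | 0.36/1.0 | 0.399 | 0.417 | 0.477 |
| 30%/30% | 0.36/1.0 | 0.442 | 0.470 | 0.583 |
| 15%/15% | 1.0/0.1 | 0.346 | 0.340 | 0.320 |
| 15%/15% | 1.5/0.36 | 0.350 | 0.346 | 0.341 |
| 5%/25% | 0.1/0.1 | 0.345 | 0.339 | 0.334 |
| 15%/15%, gamma frailty variance 1 | 0.36/0.36 | 0.501 | 0.461 | 0.541 |

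A second set of fits spread follow-up evenly over 30-1100 days, with the off-product hazard equal to placebo. Planned versus capped was 0.380 vs 0.386, 0.40 vs 0.411 and 0.424 vs 0.438 at 10%, 20% and 30% per year.

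Planned minus capped therefore runs from 0.442 - 0.470 = -0.028 to about +0.006 without frailty, and is 0.501 - 0.461 = +0.040 with it. The frailty gap is not caused by unequal follow-up: with frailty and no discontinuation it is 0.500 vs 0.442. It arises because placebo children still flare-free after Week 52 are a low-risk remnant.

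**5. Scale.** With 37 flares as a yardstick, the SE of the log HR is about 2/√37 = 0.33. The largest gap without frailty is ln(0.470/0.442) = 0.061, about a fifth of an SE.

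**The case against.** The strongest reply is that little hangs on this. Estimand 5 is supplementary. The stopping boundaries and the primary conclusion rest on Estimand 1, and the only thing the Estimand 5 result triggers is Sensitivity Analysis 2. Using all collected data is a defensible reading of treatment policy, and the numerical effect of a cap is small. All of that stands. It limits the stakes but does not remove the mismatch between label and risk period.

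The SAP also has a partial remedy. Sensitivity Analysis 2 imputes children censored under Estimand 5 out to last subject last visit (or Day + 378 if later, for extension enrollees), with a separate sensitivity parameter for each arm. That partly restores a common horizon. But it runs only if the primary analysis shows superiority and Supplementary Analysis 2 is consistent with it. Its parameter varies by arm and not by product status, and treatment is the only covariate in the Weibull model (Appendix 5).

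A reader might infer that the rule flatters tofacitinib. The documents do not support that. They give no discontinuation rates or off-product hazards. Off-product children may receive tofacitinib in the extension (Protocol 3.3: "intent is to make tofacitinib available to pediatric subjects through Study A3921145") or unrestricted standard of care (6.7.1). If off-product hazards converge between arms, the planned rule does give a stronger effect than following everyone to study end (0.374 vs 0.416). With other patterns the sign reverses (0.346 vs 0.320). Full follow-up is also not what a cap delivers. Against the cap, the planned rule is the weaker one when frailty is present.

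**Conclusion.** The point holds as a problem of coherence and interpretation. Estimand 5 disregards product discontinuation by definition, but its follow-up length depends on it, and after about Day 378 it is essentially an on-product comparison. This follows from the text alone.

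Up to about a third of flares are involved on the design inputs with no other exits, and roughly 18-25% in the scenarios with discontinuation or remission shown above. The direction of any bias is undetermined. The change in HR against a Week 52 cap is probably about 0.01-0.03 under assumed discontinuation of 10-30% per year without frailty, and about 0.04 in the opposite direction with frailty. On-product follow-up should not be described as running to study end for everyone, since remission also ends it.

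**What to change.** In SAP 5.3.1.1, end the Estimand 5 risk period, for every child in both arms, at the earlier of last contact (as extended for extension enrollees) and Randomization Day + 378. Label the result the treatment-policy effect through Week 52. Align SAP 2.3.3, Sensitivity Analysis 2 in 6.1.2.2, Table 4 and Appendix 5, so that imputation also stops no later than Randomization Day + 378. Keep the uncapped, all-data version as a sensitivity analysis. In the same edit, say how remission completers who enter the extension before Week 52 are handled, because 5.3.1.1 mentions only children who withdraw early.

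Cost: one sentence plus matching edits. The capped analysis loses the flares after Week 52. If that is a third of them, the interval on the log HR widens by about √(39.75/26.55) = 1.22, or 1/√0.68 = 1.21 on the 32% figure, so by roughly 20% at most. Retaining the uncapped version means no collected flare goes unreported. The primary test, alpha and power are unaffected.
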